G351.00	Subsequent myocardial infarction of inferior wall
G353.00	Subsequent myocardial infarction of other sites
G35X.00	Subsequent myocardial infarction of unspecified site
14A3.00	H/O: myocardial infarct
14A4.00	H/O: myocardial infarct >60
3232.00	ECG: old myocardial infarction
3235.00	ECG: subendocardial infarct
323Z.00	ECG: myocardial infarct NOS
889A.00	Diab mellit insulin-glucose infus acute myocardial infarct
G307100	Acute non-ST segment elevation myocardial infarction
G312.00	Coronary thrombosis not resulting in myocardial infarction
G36..00	Certain current complication follow acute myocardial infarct
G360.00	Haemopericardium/current comp folow acut myocard infarct
G364.00	Rupture chordae tendinae/curr comp fol acute myocard infarct
G365.00	Rupture papillary muscle/curr comp fol acute myocard infarct
G384.00	Postoperative subendocardial myocardial infarction
Gyu3100	[X]Other current complicatns following acute myocard infarct
Gyu3400	[X]Acute transmural myocardial infarction of unspecif site

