8.1.2 Safety and effectiveness outcomes

- To study the occurrence of hospitalization or referral to a specialist from primary care for three bleeding events (primary safety outcomes): (a) intracranial haemorrhage, (b) gastrointestinal bleeding and (c) urogenital bleeding among users of rivaroxaban (for DVT/PE treatment, SPAF and ACS) in comparison with individuals receiving current standard of care.

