9.3.2 Safety and effectiveness outcomes

For each outcome, potential cases will be identified using diagnostic Read codes ([Annex 3](#)) and, where appropriate, computerized patient profiles (including any free text comments) will be reviewed with all identifying information removed. Diagnostic confirmation using patients' original medical records will be performed where possible. When required, information contained in HES among the subset of practices linked to THIN, will be used.

For the purpose of this study, clinically relevant bleedings will be defined as bleedings leading to hospital admission or referrals to a specialist. This restriction is needed to minimize differential misclassification caused by the variability in patients' behavior in seeking care for less severe bleedings. Similarly, the physicians' attitude towards recording these events may differ between new drugs and standard of care. The consequence of restricting to bleedings identified through hospitalization or referrals is that bleedings leading to death before contact with a health care professional or hospital admission might be missed. It is assumed that the number of bleeding events missed due to this restriction is small. Nevertheless, the magnitude and impact of this restriction will be assessed in another study of this PASS program (Swedish Record-linkage study).

9.3.2.1 Occurrence of intracranial haemorrhage, gastrointestinal bleeding and urogenital bleeding: case definitions

Intracranial haemorrhage (Annex 3, Table 4)

Cases of intracranial haemorrhage will be identified in patients referred to a specialist or admitted to hospital that meet the criteria for one of the three following categories:

- incident cases of intracerebral haemorrhage recorded following or in association with computed tomography, magnetic resonance imaging (MRI) or X-ray angiography, or an appropriate therapeutic procedure.
- incident cases of subarachnoid haemorrhage recorded following computed tomography, MRI, X-ray angiography or lumbar puncture, or an appropriate therapeutic procedure.
- incident cases of epidural, dural, subdural and arachnoid haemorrhage recorded following computed tomography, MRI, X-ray angiography or lumbar puncture, or an appropriate therapeutic procedure.

Gastrointestinal bleeding (Annex 3, Table 5)

A patient will have to meet the following criteria to be considered a case of gastrointestinal bleeding:

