- the specific site of bleeding originating in the upper or lower gastrointestinal tract or, more specifically, in the oesophagus, stomach, duodenum, jejunum, ileum, colon or rectum.
- for upper gastrointestinal bleeding, the lesion type being erosion, gastritis, duodenitis or peptic (gastric or duodenal) ulcer.
- the lesion type being NOT related to cancer.
- the patient having been referred to a specialist or admitted to hospital.

Urogenital bleeding (Annex 3, Table 6)

A patient will have to meet both of the following criteria to be considered a case of urogenital bleeding:

- the specific site of bleeding originating in the urogenital tract.
- the patient having been referred to a specialist or admitted to hospital.

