9.8 Quality control

For each outcome, potential cases will be identified using diagnostic Read codes ([Annex 3](#)) and, where appropriate, computerized patient profiles (including any free text comments) will be reviewed with all identifying information removed. Diagnostic confirmation using the patients' original medical records will be performed where possible by means of sending a questionnaire to the PCP. When required, we will use the information contained in HES among the subset of THIN practices linked to THIN.

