761Jy00	Other specified operation on gastric ulcer
761Jz00	Operation on gastric ulcer nos
7627	Operations on duodenal ulcer
7627100	Suture of duodenal ulcer not elsewhere classified
7627y00	Other specified operation on duodenal ulcer
7627z00	Operation on duodenal ulcer nos
G850.00	Oesophageal varices with bleeding
G852000	Oesophageal varices with bleeding in diseases EC
G852100	Oesophageal varices without bleeding in diseases EC
J10y000	Haemorrhage of oesophagus
J107.00	Mallory-Weiss syndrome
J108.00	Mallory - Weiss tear
J573.00	Haemorrhage of rectum and anus
J573000	Rectal haemorrhage
J573011	Rectal bleeding
J573012	PRB - Rectal bleeding
J573100	Anal haemorrhage
J573.11	Bleeding PR
J573z00	Haemorrhage of rectum and anus NOS
J510900	Bleeding diverticulosis
J573.00	Haemorrhage of rectum and anus
J573000	Rectal haemorrhage

C/O, complaint of; EC, elsewhere classified; GIB; gastrointestinal bleeding; H/O, history of; LOC, loss of consciousness; O/E, on examination; NEC, not elsewhere classified; NOS, not otherwise specified; PR, per rectum; PRB, per rectal bleeding.

Table 6. Read codes for urogenital bleeding.

Read code	Description
14D5.00	H/O: haematuria
1A45.00	Blood in urine - haematuria
1A45.12	Haematuria - symptom
K032100	Recurrent benign haematuria syndrome
K0A2.00	Recurrent and persistent haematuria
K0A2000	Recurrent+persistnt haematuria minor glomerular abnormality
K0A2100	Recur+persist haematuria
K0A2200	Recur+persist haematuria difus membranous glomerulonephritis
K0A2300	Recur+persist haemuria df mesangial prolif glomerulonephritis
K0A2400	Recur+persist haemuria df endocaply prolifrtv glomeruloneph
K0A2500	Recur+persist hmuria df mesangiocapillary glomerulonephritis
K0A2600	Recurrent and persistent haematuria
K0A2700	Recur+persist haematuria difus crescentic glomerulonephritis
K197.00	Haematuria
K197.11	Traumatic haematuria
K197.12	Essential haematuria
K197000	Painless haematuria
K197100	Painful haematuria
K197200	Microscopic haematuria
K197300	Frank haematuria
K197400	Clot haematuria
K53y600	Haematosalpinx
K544.00	Haematometra
K595.11	Intermenstrual bleeding - regular
K596.00	Metrorrhagia
K596.11	Intermenstrual bleeding - irregular
K597.00	Postcoital bleeding
K59A.00	Premenopausal postcoital bleeding
K59B.00	Postmenopausal postcoital bleeding
K59y.11	Metropathia haemorrhagica
K59y000	Retained menstruation
K59yx00	Dysfunctional uterine haemorrhage NOS
K59yx11	Dysfunctional uterine bleeding
K59yy00	Functional uterine haemorrhage NOS

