K5C2.00	Haematocolpos
K5E..00	Other abnormal uterine and vaginal bleeding
K5Ez.00	Abnormal uterine and vaginal bleeding
Kyu9D00	[X]Other specified abnormal uterine and vaginal bleeding
158..12	Vaginal bleeding
1584.00	Heavy episode of vaginal bleeding
7F22700	Pack to control postnatal vaginal bleeding
7F22711	Pack to control postnatal vaginal bleeding
K56y111	Bleeding - vaginal NOS
K56y112	BPV - Vaginal bleeding
K595.00	Ovulation bleeding
K59y.00	Other menstruation disorders
K59yz00	Other menstruation disorder NOS

Read code	Description
K5E2.00	Abnormal vaginal bleeding

BPV, bleeding per vagina; H/O, history of; NOS, not otherwise specified.

Table 7. Read codes for “other bleeding” leading to hospitalization will be provided on request.

Table 8. Read codes for non-infective liver disease/acute liver injury.

Read code	Description
44d2.00	Liver Function Tests Abnormal
44E2.00	Serum Bilirubin Raised
44g2.00	Liver Enzymes Abnormal
J60..00	Acute And Subacute Liver Necrosis
J600.00	Acute Necrosis Of Liver
J600000	Acute Hepatic Failure
J600011	Acute Liver Failure
J600100	Acute Hepatitis - Noninfective
J600200	Acute Yellow Atrophy
J600z00	Acute Necrosis Of Liver Nos
J601.00	Subacute Necrosis Of Liver
J601000	Subacute Hepatic Failure
J601100	Subacute Hepatitis - Noninfective
J601200	Subacute Yellow Atrophy
J601z00	Subacute Necrosis Of Liver Nos
J60z.00	Acute And Subacute Liver Necrosis Nos
J622.00	Hepatic Coma
J622.11	Encephalopathy - Hepatic
J625.00	[X] Hepatic Failure
J625.11	[X] Liver Failure
J62y.11	Hepatic Failure Nos
J62y.12	Liver Failure Nos
J62y.13	Hepatic Failure
J633.00	Hepatitis Unspecified
J633000	Toxic Hepatitis
J633z00	Hepatitis Unspecified Nos
J635.00	Toxic Liver Disease
J635000	Toxic Liver Disease With Cholestasis
J635100	Toxic Liver Disease With Hepatic Necrosis
J635200	Toxic Liver Disease With Acute Hepatitis
J635X00	Toxic Liver Disease, Unspecified
J636.00	Central Haemorrhagic Necrosis Of Liver
J63y.00	Other Specified Liver Disorder
J63y100	Nonspecific Reactive Hepatitis
J63yz00	Other Specified Liver Disorder Nos
J66y600	Obstructive Jaundice Nos
R024.00	[D]Jaundice (Not Of Newborn)
R024000	[D]Cholaemia Nos
R024100	[D]Icterus Nos
R024111	[D]Jaundice
R024z00	[D]Jaundice (Not Of Newborn) Nos
R148.00	[D]Abnormal Liver Function Test
R148000	[D]Abnormal Liver Scan
R148.11	[D]Lft's Abnormal
R148z00	[D]Abnormal Liver Function Test Nos
7804200	Open Wedge Biopsy Of Lesion Of Liver
7807000	Diagnostic Laparoscopic Examination And Biopsy Liver LESION

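### The urogenital bleeding code list has no specific term for heavy menstrual bleeding or for non-postcoital postmenopausal bleeding, so this primary safety outcome is ascertained incompletely, to an unknown degree

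*Protocol*

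**What the plan says.** Protocol section 8.1.2 names the primary safety outcomes as "a) intracranial haemorrhage, (b) gastrointestinal bleeding and (c) urogenital bleeding among users of rivaroxaban".

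Section 9.3.2.1 sets two criteria for a urogenital case: "the specific site of bleeding originating in the urogenital tract" and "the patient having been referred to a specialist or admitted to hospital". Neither menstrual nor postmenopausal bleeding is excluded.

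Section 9.3.2 says how cases are found: "potential cases will be identified using diagnostic Read codes", with a pointer to Annex 3. Section 9.8 repeats this. Profile review, questionnaires to the practice and, when required, Hospital Episode Statistics (HES) in linked practices are described after that step.

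Annex 3, Table 6 lists the urogenital codes. Its only entry specific to bleeding after the menopause is "Postmenopausal postcoital bleeding" (K59B.00). Its only entry for heavy bleeding is "Heavy episode of vaginal bleeding" (1584.00), which does not name menstruation. It also has generic entries such as "Other abnormal uterine and vaginal bleeding" (K5E..00).

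**The concern.** The code list is narrower than the definition it serves. A woman referred for postmenopausal bleeding, or admitted with menorrhagia, meets both criteria of the case definition. If her record carries only the specific diagnostic term, no Table 6 code picks her up, and no later step is described that would find her. Section 9.2 admits patients of both sexes from age 2 upwards, so menstruating and postmenopausal women are both in the source population.

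The omission does not look deliberate. The table includes ovulation bleeding, intermenstrual bleeding, retained menstruation, haematocolpos and postnatal packing, so minor menstrual and gynaecological events were meant to be in scope. The protocol gives no reason for leaving out the two specific terms.

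At stake are the incidence of a primary safety outcome, which would be too low, and possibly its rate ratio, if the drugs differ in their effect on uterine bleeding.

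**Working it through.** The plan gives no figure on this point to reproduce. The check is a search of the list, followed by an illustration on assumed values.

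**1. What Table 6 contains.** All 48 rows were searched by text: 21 are haematuria terms and 27 are gynaecological.

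| Search stem | Rows | What they are |
|---|---|---|
| menorrhag | 0 | none |
| period | 0 | none |
| heavy | 1 | 1584.00, vaginal |
| menopaus | 2 | K59A.00 and K59B.00, both postcoital |
| menstru | 5 | two intermenstrual, one retained, two residual categories (K59y.00, K59yz00) |
| uterine | 6 | dysfunctional, functional and abnormal bleeding |
| vaginal | 10 | mostly unspecified or abnormal bleeding |

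Stems and their sub-codes are itemised separately (K59y.00 beside K59y000, K59yx00, K59yy00 and K59yz00; K5E..00 beside K5E2.00 and K5Ez.00). A listed stem therefore cannot be assumed to bring in unlisted terms.

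**2. Whether another route recovers the event.**
- Profile review and questionnaires apply to potential cases, that is, to patients already found by code.
- HES is used when required, only in linked practices, and is not described as a case-finding step.
- The secondary outcome of other bleeding (sections 8.2 and 9.3.2.2) requires admission, so a bleed that led only to referral cannot enter there. Its codes (Table 7) are available on request and not shown, so whether an admitted case would count cannot be judged.

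**3. Effect on the rate ratio.** The protocol gives no frequencies by type of bleed, so every input here is an assumption: genital bleeds are g = 0.30 of true comparator events, the rate ratio (RR) is 2.0 for genital and 1.0 for urinary bleeds, and a fraction f of genital events is missed in both cohorts.

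Observed RR = [(1 − g) × 1.0 + g(1 − f) × 2.0] / [(1 − g) + g(1 − f)]

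- f = 0: (0.70 + 0.60) / 1.00 = 1.30
- f = 0.10: (0.70 + 0.54) / 0.97 = 1.24 / 0.97 = 1.28
- f = 0.25: (0.70 + 0.45) / 0.925 = 1.15 / 0.925 = 1.24
- f = 0.50: (0.70 + 0.30) / 0.85 = 1.00 / 0.85 = 1.18; comparator events fall by 15%
- f = 2/3: (0.70 + 0.20) / 0.80 = 0.90 / 0.80 = 1.13; comparator events fall by 20%

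**4. A second parameterisation.** Let m be the missed share of comparator events, with RR 1.0 among captured types. The study then shows 1.0, while the RR for all urogenital bleeds is (1 − m) + m × RR_missed:

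| RR_missed | m = 0.1 | m = 0.3 | m = 0.5 |
|---|---|---|---|
| 1.0 | 1.00 | 1.00 | 1.00 |
| 1.5 | 1.05 | 1.15 | 1.25 |
| 2.0 | 1.10 | 1.30 | 1.50 |

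**5. The no-bias case.** If missed and captured types share one ratio, it cancels. With RR 1.30 for both and 15% of events lost, (0.85 × 1.30) / 0.85 = 1.30. The cost is precision: the standard error of the log rate ratio grows by √(1/0.85) = 1.085, about 8%, and each crude rate is 15% too low.

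**The case against.** The strongest reply is that Table 6 is not thin on genital bleeding. More of its rows are gynaecological (27) than urinary (21), and they include unspecified vaginal bleeding (158..12, K56y111, K56y112), "Heavy episode of vaginal bleeding", abnormal vaginal bleeding (K5E2.00), dysfunctional uterine bleeding (K59yx11), metrorrhagia (K596.00) and two residual menstrual categories. Either example patient would be found under any of these. This stands, and it limits the claim: the loss is confined to records that carry only an unlisted term.

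A reader might infer from the gap that the outcome misses the main genital bleeds in women, or that what remains is mostly haematuria. The documents do not support that. They give no distribution of bleeds by type and no information on which codes practices use, and the generic rows contradict the idea that the genital part goes largely unexamined.

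It can also be said that the protocol never states that Read codes are the only route, and that section 9.1 mentions cross-validation against HES in a subgroup of practices. This softens the gap but does not close it, because HES is neither available for all practices nor set up to find cases.

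Finally, the illustration depends on a chosen contrast between genital and urinary ratios. That is correct, which is why the equal-ratio case is shown beside it.

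**Conclusion.** The narrow point holds. Table 6 has no specific term for menorrhagia or heavy menstrual bleeding, and none for postmenopausal bleeding other than postcoital, while the case definition covers both. Followed as written, the plan ascertains a primary safety outcome incompletely, by an amount that cannot be estimated from the protocol.

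The understatement of incidence does not depend on any assumption about relative effects; it needs only that some of these bleeds are recorded solely under an unlisted term. Bias in the rate ratio is conditional: it arises only if the ratio differs between missed and captured events. The fall from 1.30 to 1.18 shows the mechanism on assumed values and is not an estimate for this study. Adjustment for age and sex (section 9.7.2.1) cannot restore events that were never captured.

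This is not detail left for a later document: Table 6 is printed as a list of codes, unlike Table 7, and Annex 1 names no stand-alone documents.

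**What to change.** Before case identification starts, do one of the following:

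- Add to Table 6 the Read terms for menorrhagia or heavy menstruation and for postmenopausal bleeding, keeping the referral or admission criterion unchanged; or
- if these bleeds are left out on purpose, narrow the urogenital case definition in section 9.3.2.1 to say so and give the reason.

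The first option costs a code-list amendment and more patient profiles to review. Some of the added bleeds will have benign gynaecological causes in both cohorts.

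Reporting urinary and genital bleeding separately beside the composite, with women's person-time as the denominator for the genital part, would make any dilution visible. It is optional and does not replace the code-list correction.
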